15.2 Statistical and Data Analysis

Availability of case and justification of sample size. According to our co-investigator and breast pathologist, the surgeons at our cancer center operated 24 cases of DCIS in 2013.

Ages	# of patients at UT Health San Antonio Mays Cancer Center
< 50	7
50-59	10
> 60	7

We consider about 60-70% enrollment in 5-year recruitment duration, we shall be able to recruit about 50-60 patients with menopausal status clinically confirmed. Tissue from this study will be compared to DCIS specimens from patients not treated with rapamycin. These specimens will be collected through the ongoing biorepository.

Statistically significant differences of the histopathological parameters and the molecular markers between the core biopsy and surgical specimens due to the rapamycin treatment will be tested by Mantel-Haenszel test for categorical data with scores ranging from 0 to 4 (or higher) as shown in Figure 2. To reach statistical power >70%, a patient group size of 24 or more is required for us to detect the difference of a score of 0.3 between untreated biopsy and treated surgical specimens with the P value targeted at 0.05 for one-sided Mantel-Haenszel test.

The **Mantel-Haenszel test** (between Rapamycin treatment & non-participant patients) will be set up as follows.

No Rapamycin # of patients (c) # of patients (d) c/(c+d)

Test between treatment & non-participant patients				
Study		IHC score ≤ 2	IHC score > 2	Percentage
UT Health San Antonio	Rapamycin	<pre># of patients (a)</pre>	# of patients (b)	a/(a+b)

Mantel-Haenszel test will allow us to extend IHC score to full range (instead of dichotomizing the IHC score), as well as other sites if more patients will be enrolled at different sites (we will not lump all patients together into one group, in case the underlying population demographic is a concern at different enrollment sites). Significance will be determined at p-value < 0.05 (Chi-square distributed with one degree of freedom). During the recruitment period, we will monitor the IHC scores different from two groups (treated/untreated) with simple *t* test on average IHC score (across all patients within each group) for each marker, in order to assess the IHC effectiveness, enrollment progress and patient demographic parameters and their association to final study outcomes.

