For statistical test within either treatment or control arm, we will use **McNemar's test** to examine IHC score differences between biopsy and surgical tissues (at significance level of 0.05). The 2x2 table set up as follows.

Test within treatment or no treatment

After treatment

		IHC score ≤ 2	IHC score > 2
Before treatment	IHC score ≤ 2	# of patients with	# of patients with
		lower IHC scores before & after	higher IHC score after treatment
	IHC score > 2	# of patients with	# of patients with
		lower IHC score after treatment	higher IHC scores before & after

Similar to between arm test, during the recruitment period, we will monitor the IHC scores different within each arm with simple paired-*t* test on average IHC score difference for each marker, in order to assess the IHC effectiveness, enrollment progress and patient demographic parameters and their association to final study outcomes.

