unexpected (in terms of nature, severity, or frequency) given (a) the research procedures that are described in the protocol-related documents, such as the IRB-approved research protocol and informed consent document; and (b) the characteristics of the subject population being studied (note: the unfounded classification of a serious adverse event as "anticipated" constitutes serious non-compliance); definitely related or probably related to participation in the research; and suggests that the research places subjects or others at a greater risk of harm (including physical, psychological, economic, or social harm) than was previously known or recognized

d. Reporting Requirements

For this study, the Master Adverse Events Documents collected on patients for this protocol will be reviewed by the PI on a monthly basis to determine if a serious safety problem has emerged that result in a change or early termination of a protocol such as:

- 1. dose modification,
- 2. suspending enrollment due to safety or efficacy, or
- 3. termination of the study due to a significant change in risks or benefits.

AE's and SAE events that occur during clinical trials with or without an Investigational New Drug (IND) application are mandatory reports submitted to FDA via **Medwatch FDA F3500A within 15 days for events that have at least a possible relationship with the drug.**

e. Assuring Compliance with Protocol and Data Accuracy

As with all studies conducted at UT Health San Antonio Mays Cancer Center, the PI has ultimate responsibility for ensuring protocol compliance, data accuracy/integrity and responding to recommendations that emanate from monitoring activities. The research site will be audited for accuracy at the end of the treatment cycle for the first patient enrolled. Protocol compliance, data accuracy and reporting of events is further ensured by an annual audit conducted by the Data Safety Officer, whose audit report is shared with the PI, the research team, and will be reviewed by the UT Health San Antonio Mays Cancer Center DSMB.

f. UT Health San Antonio Mays Cancer Center DSMB Membership

The UT Health San Antonio Mays Cancer Center has two DSMB's with a primary set of members specific to the histology of the study consisting of UT Health San Antonio faculty and staff. This Protocol is under the jurisdiction of DSMB#2 for Solid Tumor Studies.

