- 4. plans for changing frequency of interim analysis as well as procedures for recommending protocol changes;
- 5. recommendation of dose escalation, MTD recommendation of early termination based on efficacy results;
- 6. recommendation of termination due to unfavorable benefit-to-risk or inability to answer study questions;
- 7. recommendation of continuation of ongoing studies;
- 8. recommend modification of sample sizes based on ongoing assessment of event rates; and
- 9. review of the final results and publications.

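### Interim efficacy t tests of unspecified number and consequence, with no fixed final-analysis point, mean the final p<0.05 is not assured to be a 5% test

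*Combined protocol and SAP*

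**What the plan says.** **Interim tests.** Section 15.2 states: "During the recruitment period, we will monitor the IHC scores different from two groups (treated/untreated"), by a t test on the mean score for each marker. For the before-and-after comparison it adds: "during the recruitment period, we will monitor the IHC scores different within each arm", by a paired t test for each marker. The stated purpose is to follow how the IHC performs, enrolment, demographics and their association with outcome. No number of looks, timing or consequence is given.

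**Final tests.** The between-group Mantel-Haenszel test is read as follows: "Significance will be determined at p-value < 0.05 (Chi-square distributed with one degree of freedom"). McNemar's test within each arm is also read at 0.05.

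**Size.** "To reach statistical power >70%, a patient group size of 24 or more is required". Section 15.2 forecasts about 50-60 patients over five years and allows for further sites.

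**Oversight (Appendix 2).**
- Part b has DSMB #2, together with the principal investigator (PI), assess treatment effects as well as adverse events.
- Part d lists, among the possible results of the PI's monthly review of adverse event documents, "suspending enrollment due to safety or efficacy".
- Part g lists, among DSMB functions, "recommendation of early termination based on efficacy results", changes to the frequency of interim analysis, and modification of sample size based on event rates.
- Part g also has the DSMB establish statistical monitoring guidelines after activation, if the protocol has not already set them.

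**The concern.** Reduction of malignant markers is one of the two primary objectives (Section 4.1), and the interim t tests use the same scores that will decide it. The trial is open-label, and nothing in the plan shields the investigators from the interim comparisons. Recruitment could reasonably end near 24 patients or run to 60. Neither choice would breach the plan, and either could be made after seeing the t tests.

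If a favourable look can lead to stopping and a less favourable one to continuing, a final test at 0.05 no longer has a 5% false-positive rate. The estimated effect in a trial stopped that way would also tend to be too large. The plan contains no boundary, no alpha spending, and no statement that the looks are descriptive only. Following accrual, assay performance or demographics does not require a treated-versus-untreated test.

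**Working it through.** **Inputs from Section 15.2.** Final level 0.05; group size at least 24; forecast 50-60 (midpoint 55); t tests during recruitment, number not stated.

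**Assumptions.** The number and spacing of looks; equal groups (no control-group size is stated); normal scores; the trial ends with a positive claim at the first nominal p<0.05.

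**The plan's own figure.** The group size of 24 cannot be reproduced because no SD or score distribution is given. Read as a paired comparison, one-sided 0.05 and 70% power imply SD = 0.3 × √24 / (1.645 + 0.524) ≈ 0.68. The type I error results below do not depend on this SD.

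**Step 1: two looks, by formula.** With looks at n1 and n2 the two statistics have correlation √(n1/n2). The overall two-sided error is 1 − Pr(|Z1| < 1.96 and |Z2| < 1.96).
- For 24 and 55 the correlation is √(24/55) = 0.66. The error is 8.5% two-sided, or 8.2% one-sided with 1.645.
- For 24 and 60 the correlation is √(24/60) = 0.63. The error is 8.6% two-sided, or 8.3% one-sided.

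**Step 2: simulation under no effect.** Paired and two-sample t tests, 60,000 runs per scenario. Each range covers both designs, one-sided and two-sided.

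| Looks (patients per group, or pairs) | Type I error, one marker |
|---|---|
| Final analysis only | 5% |
| 24, 55 | 8-9% |
| 24, 33, 44, 55 | 10-11% |
| 11, 22, 33, 44, 55 | 13-15% |
| Every 3 from 24 to 60 | 13-15% |
| Every patient from 24 to 60 | 14-17% |

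**Step 3: closer to the planned final test.** With scores on a 0-4 scale (distribution assumed), interim t tests and a final Mantel-Haenszel chi-square at 60 per group, the error is 8.5% with two looks and 14.5% with five. The result does not depend on using a t test at the end.

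**Step 4: looks that change nothing.** In the same simulations the final test taken alone rejects in about 5% of runs. The excess comes entirely from acting on a look.

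**Step 5: boundary for one look at half the patients.** O'Brien-Fleming critical values are c√2 at the look and c at the end, with c chosen so that overall error is 5%.
- Two-sided: c = 1.977, giving nominal levels of about 0.005 and then 0.048.
- One-sided 0.05: c = 1.678, giving about 0.009 and then 0.047.

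**The case against.** The strongest reply is that Section 15.2 attaches no decision to the t tests and describes them as a check on the assay, enrolment and demographics. Looks that change nothing cost nothing, as Step 4 shows. The efficacy wording in Appendix 2 is also weaker than it first appears:
- The suspension item belongs to a monthly review of adverse event documents aimed at detecting a serious safety problem. IHC scores are not among the listed contents of those documents.
- The termination item shares a line with dose escalation and MTD, which do not apply to a single-dose trial, so it reads as general charter text.
- The DSMB's powers are recommendations, and no text says that it receives the Section 15.2 t tests.
- The DSMB is to set monitoring guidelines later, so error control is deferred rather than ruled out.
- Recruitment is planned over five years, so size is not wholly open-ended.

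All of this stands, and it limits the claim. A reader might infer that the plan links the t tests to an efficacy stop, or that the final test is certainly not a 5% test. The documents support neither.

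A reader might also expect much larger figures. About 26% two-sided requires looks every three patients starting from 3 per group, far below the plan's minimum of 24. About 37% requires three independent markers with five looks, and three such markers already give 14% with no interim look (1 − 0.95³). Multiplicity across markers is a separate issue.

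The gap itself remains. The tests are planned, nothing declares them non-binding, the DSMB and the PI assess treatment effects, no boundary exists, and the final-analysis point is not fixed.

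**Conclusion.** The concern holds in a conditional form: following the plan does not assure that the final p<0.05 is a 5% test. If a look at nominal p<0.05 can end the trial with a positive claim, type I error per marker is about 8-9% with looks at 24 and 55 per group. It is about 13-15% with five looks or with looks every three patients from 24 onward. Testing after every patient from 24 to 60 would add a little more, up to about 17%.

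These figures rest on assumed numbers of looks, equal groups and stopping at the first nominal significance. The documents settle none of these, and the lower bound is 5% if the looks are never acted on. The change is worth making before analysis because it is cheap and because, once unblinded comparisons have been seen, their influence on when recruitment ended cannot be reconstructed.

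**What to change.** 1. **Section 15.2:** limit monitoring during recruitment to accrual, assay success and score distributions pooled over treated and untreated specimens, with no treated-versus-untreated or paired p-values.
2. **Section 15.2 and Appendix 2:** state that in this study no early stop, suspension or sample-size change will be based on efficacy results. A study-specific sentence is enough; the institutional text need not be rewritten.
3. **Section 15.2:** fix the number of evaluable patients, or the calendar date, at which the single final analysis is done.
4. **If an efficacy look is wanted:** prespecify one, with an O'Brien-Fleming boundary computed for the same sidedness as the final test. For two-sided 0.05 with one look at half the patients, the levels are about 0.005 and then 0.048. Sidedness must be settled first, because the sizing is one-sided ("with the P value targeted at 0.05 for one-sided Mantel-Haenszel test") while the final test is a one-degree-of-freedom chi-square, which is two-sided by construction.

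The cost is wording in two places and the loss of an informal early read on efficacy. Safety monitoring is unchanged.

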16. ADVERSE EVENTS REPORTING

Adverse event data collection and reporting, which are required as part of every clinical trial, are done to ensure the safety of subjects enrolled in the studies as well as those who will enroll in future studies using similar agents. Subjects must be carefully monitored for AEs. Adverse events should be assessed in terms of their seriousness, intensity, and relationship to the study drug. Adverse events are reported in a routine manner at scheduled times during a trial. Additionally, certain adverse events must be reported in an expedited manner to allow for optimal monitoring of patient safety and care.

All patients experiencing an adverse event, regardless of its relationship to study drug, will be monitored until:

- 1. the adverse event resolves or the symptoms or signs that constitute the adverse event return to baseline;
- 2. there is a satisfactory explanation other than the study drug for the changes observed; or
- 3. death occurs.

16.1 Definitions & Descriptions

16.1.1 Adverse event (AE)

An adverse event (AE) is any untoward medical occurrence in a patient receiving study treatment and which does not necessarily have a causal relationship with this treatment. An AE can, therefore, be any unfavorable and unintended sign (including an abnormal laboratory finding), symptom, or disease temporally associated with the use of an experimental intervention, whether or not related to the intervention. A "drug-related toxicity" includes as events, any toxicity considered related, probably related, or possibly related to study drugs. Toxicities clearly not related to the drug, such as disease progression, environmental, unrelated trauma may not be considered "drug related toxicity".

16.1.2 Severity of AEs

All adverse events will be graded according to the NCI Common Terminology Criteria for Adverse Events (CTCAE) version 4.03. The CTCAE v. 4.03 is available at: http://evs.nci.nih.gov/ftp1/CTCAE/CTCAE_4.03_2010-06-14_QuickReference_5x7.pdf

If no CTCAE grading is available, the severity of an AE is graded as follows:

• Mild (grade 1): the event causes discomfort without disruption of normal daily activities.

- Moderate (grade 2): the event causes discomfort that affects normal daily activities.
- Severe (grade 3): the event makes the patient unable to perform normal daily activities or significantly affects his/her clinical status.
- Life-threatening (grade 4): the patient was at risk of death at the time of the event.
- Fatal (grade 5): the event caused death.

16.1.3 Serious Adverse events

All SAEs, regardless of attribution, occurring during the study or within 30 days of the last administration of study drug must be reported upon discovery or occurrence. Additional expedited or routine reporting may be required, depending on the nature of the SAE. A "serious" adverse event is defined in regulatory terminology as any untoward medical occurrence that:

- 1. Results in death. If death results from (progression of) the disease, the disease should be reported as the event (SAE) itself.
- 2. Is life-threatening. The patient was at risk of death at the time of the event; it does not refer to an event that hypothetically might have caused death if it were more severe.
- 3. Requires in-patient hospitalization or prolongation of existing hospitalization for \ge 24hours.
- 4. Results in persistent or significant disability or incapacity.
- 5. Is a congenital anomaly/birth defect.
- 6. Is an important medical event.
- 7. Any event that does not meet the above criteria, but that in the judgment of the investigator jeopardizes the patient, may be considered for reporting as a serious adverse event. The event may require medical or surgical intervention to prevent one of the outcomes listed in the definition of "Serious Adverse Event". Examples: allergic bronchospasm requiring intensive treatment in an emergency room or at home; convulsions that may not result in hospitalization; development of drug abuse or drug dependency.

16.1.4 Exceptions to the Definition of SAE

Certain hospitalizations or prolongation of hospitalizations should not be considered SAEs, including those that meeting the following criteria:

- 1. An admission resulting in a hospital stay of less than 24 hours.
- 2. An admission that is pre-planned (i.e. elective or scheduled surgery arranged prior to the start of the study).
- 3. An admission that is not associated with an AE (i.e. social hospitalization for purposes of respite care).

16.1.5 Unanticipated Problems Involving Risks to Subjects or Others (UPIRSO)

A UPIRSO includes events that meet ALL of the following criteria:

- 1. Are unanticipated in terms of nature, severity, or frequency;
- 2. Place the research subject or others at a different or greater risk of harm; AND
- 3. Are deemed to be related or possibly related to participation in the study.

16.2 Adverse event reporting

Steps to determine if expedited reporting is required include all events that occur within 30 days of the last dose of protocol treatment. Any event that occurs more than 30 days after the last dose of treatment

and is attributed (possibly, probably, or definitely) to the agent, must also be reported accordingly. You are required to:

- 1. **Identify** the type of adverse event using the NCI CTCAE v 4.03.
- 2. **Grade** the adverse event using the NCI CTCAE v 4.03.
- 3. **Determine** whether the adverse event is related to the protocol therapy.

Attribution categories are as follows:

Definite: AE is clearly related to the study treatment (attribution should be separated by each study drug) **Probable:** AE is likely related to the study treatment (attribution should be separated by each study drug) **Possible:** AE may be related to the study treatment (attribution should be separated by each study drug) **Unrelated:** AE is clearly NOT related to the study treatment (attribution should be separated by each study drug) study drug

Determine the prior experience of the adverse event. Expected events are those that have been previously identified as resulting from administration of the specific agent. An adverse event is considered unexpected, for expedited reporting purposes only, when either the type of event or the severity of the event is not listed in the current protocol and/or the drug package insert.

16.3 Expedited SAE Reporting

All SAEs must be reported following the DSMP outlined in *Appendix 2* of this protocol within 24 hours of becoming aware of the event. Completion of the UT Health San Antonio Mays Cancer Center SAE Form is required. The completed form should assess whether or not the event qualifies as a UPIRSO. The report should also include:

- 1. Protocol description and number
- 2. Patient's Identification Number
- 3. Description of event, severity, treatment, and outcome if known
- 4. Supportive laboratory results and diagnostics
- 5. Hospital Discharge Summary (if available)

All SAEs will be reported to, and reviewed by, the DSMB at their next meeting.

16.4 Reporting to the UT Health San Antonio IRB

Any death of a subject that is unanticipated in nature and at least possibly related to study participation will be promptly reported to the UT Health San Antonio Mays Cancer Center Regulatory Affairs Division for reporting within 24 hours of notification. Other SAE's that are life threatening, but not fatal, should be reported to UT Health San Antonio Mays Cancer Center Regulatory Affairs within 7 days of notification.

The following SAEs will be reported to the UT Health San Antonio Mays Cancer Center Regulatory Affairs for reporting to the UT Health San Antonio IRB at the time of continuing review:

- 1. All deaths of UT Health San Antonio Mays Cancer Center subjects that were not previously reported
- 2. All deaths of non-UT Health San Antonio subjects that are deemed to be unanticipated in nature and unrelated to participation
- 3. Other UPIRSO's
- 4. All other SAEs not previously reported to the UT Health San Antonio IRB as UPIRSOs

In addition, participating sites should follow local guidelines for reporting of SAEs to their IRB as required.

16.5 Reporting to the FDA

The UT Health San Antonio Mays Cancer Center Regulatory Affairs division will notify FDA within 7 calendar days of any SAE that is associated with study treatment, is unexpected, and is fatal or life-threatening. The UT Health San Antonio Mays Cancer Center Regulatory Affairs Division will notify the FDA within 15 calendar days of any SAE that is associated with the study treatment, unexpected, and serious but not fatal or life-threatening. This includes any previous SAEs that were not initially deemed reportable, but are later determined to meet the criteria for reporting by the DSMB. In these instances, an FDA Med Watch Form will be completed.

16.6 Routine Reporting

All other adverse events, such as those that are expected, or are unlikely or definitely not related to the study participation, are to be reported on the appropriate eCRF according to the time intervals noted in the Schedule of Events. Routine AEs will be reviewed by the assigned DSMB for the study in accordance with the Mays Cancer Center's Multi-site DSMP Procedures. These will be reviewed by the DSMB on an on-going basis. A summary of all these events will be reported annually to the UT Health San Antonio IRB as part of the continuing review process.

17. STUDY MANAGEMENT

